5.6 Data Analysis

1. VAST Implementation

The primary research team will assess qualitative aspects of implementation and sustainability. With each facilitation call, whether scheduled or ad hoc, members of the primary research team will use field notes to log barriers and facilitators related to implementation. The research team will use process maps to record adaptations. Changes from the initial map will be categorized as major or minor. Further, the number of weeks each VAST required to achieve their final process map will be noted. Together, these assessments will be used to assess fidelity of implementation and to transform the Implementation Guide into a final, robust Implementation Playbook.

2. Staff Perceptions

Once the intervention period for all VASTs is complete, we will assess for differences in the VAST- vs VAST+ arms on perceived influences on Veteran care, proportion of VAST recommendations accepted, and the user experience survey.

3. Evaluation of clinical activities

Characteristics of each facility including number of beds, number of CLC beds, medical complexity group, attendance of leadership at VAST sessions and the mean number of cases discussed per session will also be compared. If significant differences are seen between VAST- and VAST+ sites, additional multivariable analyses will be conducted.

4. Facility-Level Antibiotic Use

To assess for impact of VAST on antibiotic use, we will summarize the 4 antibiotic use metrics for each site, comparing the pre- and post-implementation periods for the acute and long-term care units. Rates of overall antibiotic use (DOT/1000 DOC), broad-spectrum antibiotic use (DOT/1000 DOC) and antibiotic starts (new prescriptions/1000 DOC) will be calculated with 95% confidence intervals based on exact Poisson distributions. To summarize length of therapy in the pre- and post-implementation periods, we will calculate means and 95% confidence intervals.

To assess for differences between the VAST- and VAST+ study arms, we will use a multi-level Poisson regression model in which facilities will be

parameterized as random effects and study arm and time (year before vs. year of implementation) as fixed effects, with their interaction as the estimated effect of interest. This model will yield estimated rate ratios for overall antibiotic use, use of broad-spectrum agents (ASI ≥ 8), and antibiotic starts for each intervention arm. Length of therapy can be modeled as continuous outcomes in similarly parameterized models, with the interaction of arm and study year as the effect of interest.

Qualitative data will be analyzed in aggregate by the research team for each study activity and shared with the primary research team. We will use data describing specific goals or objectives for the VAST to assess our hypothesis.

Additionally, we will summarize and compare patient characteristics for patients with RTI or UTI. For patients in this cohort, we determine provider and facility factors that are predictive of over, under, or guideline-concordant prescribing for each diagnosis. Information collected from the CDW will be used to develop and pilot a natural language processing algorithm that detects UTIs using provider documentation. This algorithm will be developed using medical record note text stored in the CDW.

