3.0 Objectives

The **purpose** of this project is to expand the VAST to additional rural VAMCs and affiliated off-site ID clinicians. We further propose to test the influence of facility-level peer comparison through the Antibiotic Use Report (VAST + feedback) to augment changes in facility-level antibiotic use beyond the influence of the VAST alone.

Our **central hypothesis** is that feedback reports that quantify facility-level antibiotic use will enhance the efficacy of VASTs to support antimicrobial stewardship. We will use the following **specific aims** as we test this hypothesis:

Aim 1: Identify and test effective strategies for implementing the VAST. The VAST is a complex intervention that affects individuals and systems. Using the expanded framework for reporting adaptations and modifications to evidence-based interventions (FRAME), we will assess adaptations made at intervention sites and by infectious disease experts. Methods will include process maps and semi-structured interviews to gather qualitative data about what key VAST members perceive as facilitators, barriers and burden to VAST implementation. [We will also evaluate implementation costs.] We anticipate that VASTs that receive Antibiotic Use Reports (VAST+) will tailor their activities to address quantifiable antibiotic use metrics.

Aim 2: Determine the influence of the VAST overall and VAST+ on the care of Veterans with suspected infections. We will evaluate the Veteran population served, clinical activities, and user perceptions of the VAST. For a subset of patients with common infections (e.g., urinary tract infection, pneumonia, cellulitis etc.) we will assess the concordance of clinical care with recommendations from evidence-based clinical practice guidelines. User experience measures will include VAST members' perceptions of the quality and timeliness of care as well as access to input from specialty care providers. We anticipate that compared to VASTs that do not (VAST-), VASTs who receive Antibiotic Use Reports (VAST+) will report a greater perceived influence on Veteran care.

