5.0 Study Procedures

5.1 Study Design

We will conduct a Type 2 hybrid effectiveness-implementation design [37], randomizing rural VAMCs that do not have ID-trained professionals on staff to implement the VAST alone (VAST-) versus VAST + antibiotic use feedback (VAST+). We propose to test the implementation strategy, specifically assessing modification and adaptations and effectiveness, measured as the VAST's influence on Veteran care and on antibiotic use.

The 4 main activities of the study are

1. Determine modifications of **VAST implementation** through ongoing discussions with champions at the intervention sites and with the infectious disease experts.
2. Assess **staff perceptions** of the VAST using surveys and semi-structured interviews to gather qualitative data about what key VAST members perceive as facilitators, barriers and burden to VAST implementation.
3. Evaluate the **clinical activities** of each VAST. This evaluation will include using chart review to describe the patients discussed, including their clinical diagnoses, as well as acceptance of recommendations by providers. These activities will involve use of the VA's administrative databases as well as chart review.
4. Measure changes in overall **facility-level antibiotic use** for each VAST. These activities will involve extraction of antibiotic use and census data from the VA's administrative databases

Study Population

The study will include up to 10 intervention sites, which are rural VA facilities. Infectious disease experts will serve as Local Site Investigators (LSIs). Each LSI will work with at least 1 intervention site (rural VA facility) to set up a VAST.

1. VAST Implementation

For this study activity, study participants will include the participating sites.

2. Staff perceptions

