5.5 Study Evaluations

1. VAST Implementation

Randomization

To randomize rural VAMCs, we will use a matched pairs design to ensure that the total number of acute and long-term care beds is similar between the two study arms. For simplicity, if more than one rural VAMC forms a VAST with the same off-site ID expert, (e.g., both Altoona and Erie have a relationship with the Pittsburgh VAMC) we will randomize both rural VAMCs into the same arm.

VAST Members & Activities

Staff from acute (hospital) and long-term care (CLC) units will populate the team, with the intent of using more than one person with the same role to allow for fluidity among individual members. Each VAST will identify 2 to 3 champions, likely pharmacists and infection preventionists, with responsibilities that include identifying patients prescribed antibiotics and recording the VAST's recommendations in the electronic medical record. Contributions of the ID physician will include his or her clinical knowledge and experience with antimicrobial stewardship. The ID physician will identify 1-2 other individuals, such as an ID-trained clinical pharmacist, to also participate in the VAST. This will enhance continuity of the VAST during holidays, vacations, and travel. Each team will also include a field research assistant for the ID expert(s); field research assistants will help support VAST implementation and data collection.

The VAST will meet for one hour each week. As a whole, team members from the rural VAMC and off-site ID experts will participate in chart review, discussion, and making recommendations regarding the need and choice of antimicrobial agent(s), length of therapy, orders for and interpretation of microbiological cultures and diagnostic tests. At each session, the field research assistant will note the names, roles, and practice setting for each of the VAST participants; this information will be shared with the primary research team.

When feasible, the ID expert(s) will travel to the rural VAMC for a face-to-face kickoff meeting. This will facilitate team building and help set the tone for the ensuing videoconferences. Leadership support to allow time for personnel from the rural as well as the ID expert(s) VAMCs to actively engage in the VAST will be a key factor for success. Further, the presence of Chiefs or Assistant Chiefs of Staff, Medicine, Nursing, and Pharmacy from the rural VAMC, especially at the first 4 to 8 VAST sessions, will help engage other clinical staff.

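### Adjusted analyses are triggered by significance tests across at most 10 sites, and two of the five tested characteristics arise after randomisation and may be affected by the report

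*Combined protocol and SAP*

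**What the plan says.** Section 5.6, item 3 (Evaluation of clinical activities), lists what is compared between arms. It opens with "Characteristics of each facility including number of beds, number of CLC beds, medical complexity group" and continues with "attendance of leadership at VAST sessions and the mean number of cases discussed per session will also be compared". The next sentence is the rule: "If significant differences are seen between VAST- and VAST+ sites, additional multivariable analyses will be conducted". The text gives no test, significance level, outcome, covariate list or model for these analyses.

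Four other places bear on the rule:

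- **Number of sites.** Section 5.1: "The study will include up to 10 intervention sites, which are rural VA facilities".
- **Allocation.** Section 5.5 uses a "matched pairs design to ensure that the total number of acute and long-term care beds is similar between the two study arms". Where two rural sites share an ID expert, "we will randomize both rural VAMCs into the same arm", so there may be fewer independent units than sites.
- **Antibiotic-use model.** Section 5.6, item 4, specifies a multi-level Poisson model with facility random effects and fixed effects for arm and time, "with their interaction as the estimated effect of interest". It names no covariates and does not refer to the rule in item 3.
- **Expected mechanism.** Aim 1 in section 3.0 anticipates that VAST+ teams "will tailor their activities to address quantifiable antibiotic use metrics". Section 2.0 reports that pilot sites thought timelier feedback would strengthen leadership backing for staff time. Section 5.5 treats leadership support as critical to success.

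**The concern.** There are two separate problems.

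First, a significance test is a poor guide to whether adjustment matters. With about five sites per arm it misses large imbalances, and with several tests it can also fire by chance. Whether an adjusted analysis is done at all then depends largely on luck.

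Second, the list treats baseline features and process measures alike. Beds, CLC beds and complexity group are fixed before allocation. Leadership attendance and cases per session are observed afterwards, and the plan's own account of how feedback works makes both plausible consequences of the report. A between-arm difference in them may be the intervention working. Adjusting for it would remove part of the effect the trial is meant to estimate, and the rule would call for that most often when the report had changed the process most.

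**Working it through.** The supplied text states no power, alpha or target effect, so there is no planned figure to reproduce.

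**Inputs from the documents:** at most 10 sites (5.1); matched pairs (5.5); five named characteristics, three baseline and two post-randomisation (5.6).

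**Assumptions:** 1:1 allocation, hence 5 versus 5; two-sided alpha 0.05; a two-sample t-test for each continuous characteristic.

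**1. Can the trigger see a real difference?** With n sites per arm, df = 2n − 2 and the noncentrality is d/√(2/n), where d is the true difference in SD units. For n = 5, df = 8, the critical t is 2.306 and √(2/5) = 0.632. The observed difference must therefore exceed 2.306 × 0.632 = 1.46 SD to reach p < 0.05. Power from the noncentral t distribution:

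| True difference | 5 v 5 | 4 v 4 | 3 v 3 |
|---|---|---|---|
| 0.5 SD | 11% | 9% | 8% |
| 1.0 SD | 29% | 22% | 16% |
| 1.5 SD | 55% | 43% | 29% |
| 2.0 SD | 79% | 66% | 46% |

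At 5 versus 5, 80% power needs a true difference of about 2.0 SD. For a yes/no characteristic, 4 of 5 against 1 of 5 gives Fisher p = 0.21. The result also depends on the unnamed test: an exact sign-permutation test on five matched pairs has a smallest two-sided p of 2/2⁵ = 0.0625, so it could never fire at 0.05.

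**2. How often does it fire with no real difference?** For k independent tests the chance is 1 − 0.95^k. Five tests give 1 − 0.95⁵ = 22.6%; the three baseline items alone give 1 − 0.95³ = 14.3%. The 22.6% is the figure for independent tests. Total and CLC bed counts are related and total beds are matched, so the actual rate should be lower.

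**3. What happens if a process measure is adjusted for?** If a share s of the effect runs through the measure, the adjusted log rate ratio is (1 − s) × the total log rate ratio. The documents give no effect size, so take −0.15 for illustration:

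- s = 0: exp(−0.15) = 0.86
- s = 0.5: exp(−0.075) = 0.93
- s = 1: exp(0) = 1.00

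A simulation of each site's change in log rate (10 sites, assumed residual SD 0.12) gave the same values. It also applied the trigger to that one measure. If VAST+ shifts the measure by 1 SD the trigger fires in about 28% of trials; at 2 SD, in about 80%. With half the effect mediated, the rate ratio averaged over trials that follow the rule is 0.89 at a 1-SD shift and 0.92 at 2 SD.

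**4. Does this reach the antibiotic-use model?** Regressing the change in log rate on a site-level measure amounts to giving that measure a time interaction. A site-constant covariate entered only as a main effect behaves differently. In a simulated pre/post Poisson dataset the arm-by-time coefficient was −0.154 with and without such a covariate. The shift in step 3 therefore needs a covariate that varies with time or interacts with it, or an outcome with no pre-period. Section 5.6, item 2, has such outcomes: perceived influence on care, acceptance of recommendations, and the user survey.

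**The case against.** A reader might infer that the plan will adjust away the VAST+ effect on antibiotic use. The documents do not support that. The rule sits under clinical activities, calls the analyses additional, names no outcome and replaces nothing. The item 4 model is specified separately without covariates, and step 4 shows that a site-constant main effect leaves its estimate unchanged. Nor does the text say that leadership attendance or cases per session would be covariates; that is an inference from adjusting for whatever differed. All of this stands, and it limits the point.

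The concern about missed imbalance is also softened. Total beds are matched, and the pre/post comparison uses each site as its own control, so stable site differences largely cancel from the arm-by-time term. What remains is complexity group, CLC share and unlisted factors, together with the outcomes that have no pre-period.

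The mechanism can be questioned too. Section 2.0 speaks of leadership support, not attendance. Section 5.5 wants leaders present mainly at the first 4 to 8 weekly sessions, while the reports are quarterly, so much of the attendance may precede any effect of the report. Tailoring activities is not the same as discussing more cases. The process measures are therefore plausible mediators, not demonstrated ones.

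The objection does not rescue the rule itself. Followed as written, it makes adjustment depend on chance, and nothing in it excludes a measure that the report may have changed. Calling the analyses additional does not say which estimate stands if the two differ.

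**Conclusion.** The point holds in a limited form. The trigger is unreliable at this number of sites: 29% detection at 1 SD and 79% at 2 SD, and up to about 23% false firing, assuming 5 versus 5 sites, two-sided alpha 0.05 and, for the last figure, five independent tests. If the process measures enter as covariates, they can pull the arm effect toward the null for perceived influence on care, acceptance of recommendations and the user survey. For the antibiotic-use model this requires a time-varying or time-interacted covariate, which the plan neither describes nor rules out. The move from 0.86 to 0.93 or 1.00 is illustrative only, since the effect size and the mediated share are both assumed. A claim that the planned primary estimate is itself biased would go beyond the text.

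**What to change.** In section 5.6:

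1. Delete the significance trigger, and describe baseline balance by arm without tests.
2. State that the item 4 model as specified remains the primary estimate for antibiotic use.
3. Limit any adjusted analysis to one or two pre-randomisation covariates named in advance, such as total beds (the matching variable) or complexity group, and run it whatever the observed imbalance. In the item 4 model a covariate needs a time interaction to have any bearing on the arm-by-time term. The pre-period rate should not be used there, because it is already an outcome row.
4. Report leadership attendance and cases per session by arm as process outcomes, and state that they will not be covariates in any arm comparison.

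The cost is wording only, with no new data or sites. There is one small downside: with 10 or fewer sites each covariate uses a degree of freedom, so the adjusted analysis should be labelled supportive.

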Aim 3: Determine the influence of the VAST overall and VAST+ on antibiotic use at each VAMC. The primary outcome measure will be overall rates of antibiotic use. Secondary outcomes will be changes in the rates of broad-spectrum antibiotic use and antibiotic starts, and in length of antibiotic therapy. We anticipate that antibiotic use will decrease after VAST implementation at study sites and compared to VASTs that do not (VAST-), VASTs who receive Antibiotic Use Reports (VAST+) will achieve greater reduction in overall antibiotic use, and specifically in broad-spectrum antibiotics.

Relevance to Veterans and the VA

Veterans experience many of the risk factors associated with development of antimicrobial resistant and healthcare-associated infections. The unprecedented effects of the novel Coronavirus disease 2019 (COVID-19) on the health of our Veterans and on our entire healthcare system makes the demand for ID expertise even more apparent, especially in long-term care. Also, this study directly addresses the VA MISSION ACT to improve access to care, timeliness and quality of care, using telehealth services. Finally, this project is aligned with the priorities of our operation partners: VA Antimicrobial Stewardship Taskforce (ASTF), the VA National Infectious Disease Service (NIDS), VA Pharmacy Benefits Management (PBM) Services, and the Office of Rural Health.

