For this study activity, the study population will be comprised of individuals who participate in the VAST and will include VA staff members. The team members from the intervention sites will include pharmacists, infection preventionists, nurses, and prescribing clinicians. These staff are important antibiotic stewardship stakeholders. Each rural VAMC will pair with an ID expert from another VA facility to form a multidisciplinary VAST which will perform antimicrobial stewardship activities. The rural VAMCs and their affiliated ID physician will be randomized to either the VAST alone (VAST-) or VAST + feedback (VAST+), consisting of a quarterly Antibiotic Use Report describing facility level antibiotic use.

3. Evaluation of clinical activities

For this study activity, VA patients discussed during each VAST will make up the study population. Study staff will perform medical record review and utilize the VA's administrative databases to collect information about the patients. Veteran patients will not be involved in any study interventions; only chart review will be conducted.

4. Facility-level antibiotic use

We will review total antimicrobial use at the intervention sites and at control sites. These data will be accessed via VINCI.

Protection Against Risk

This is a minimal risk study. The primary risk is breach of confidentiality for patients discussed by the VAST and breach of privacy for providers who participate in semi-structured interviews.

1. VAST Implementation

For this study activity, there is no risk to patients or staff.

2. Staff Perceptions

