5.4 Inclusion/Exclusion Criteria

All sites participating in the VAST will be included. Veteran patients will be discussed during VAST calls according to clinical need. Additionally, administrative data will be collected from CDW within the VINCI environment and will be used to extract and analyze age, gender, race/ethnicity, and comorbid conditions for creation of the quarterly Antibiotic Use Reports.

1. VAST Implementation

All participating sites will be included.

2. Staff Perceptions

All staff who participate in the VAST will be invited by email to participate in a survey and a 20-60 minute telephone semi-structured interviews.

3. Evaluation of clinical activities

All patients discussed during the VAST will be included.

4. Facility-Level Antibiotic Use

Information will be collected from CDW for all participating sites.

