1. The first metric, days of antibiotic therapy per 1000 days of care (DOT/1000 DOC), measures the overall rate of antibiotic use and is a common metric that accounts for dose adjustments, including for people who receive dialysis. Administration of any dose of an antimicrobial on a given day represents a single DOT for that agent, regardless of the number of times the doses are administered or the dose strength.
2. Second, we will specifically examine the rate of broad-spectrum antibiotics, defining broad-spectrum agents as those with an Antibiotic Spectrum Index (ASI) score of ≥ 8 . This scale ranges from 1 to 13.
3. The third metric is the rate of antibiotic starts (new prescriptions), calculated as the number of starts per 1000 DOC.
4. The fourth metric is the length of antibiotic therapy in days.
 - a. For people on hemodialysis, up to 72 hours may occur between doses of specific agents (e.g. vancomycin, aminoglycosides, several cephalosporins); these will be considered as a single course.

For each site, we will calculate these statistics at monthly intervals for the 12 months prior to and the 15 months following the first VAST session, allowing for a 3-month wash-in period, to generate descriptive summaries of changes in acute care and in long-term care over time, understand month-to-month variability in these metrics, and to flag any issues with data availability or validity in the course of the

intervention given operational shifts occurring at facilities around COVID-19 treatment or the rollout of the Cerner electronic medical record across the VA.

Additionally, we will use CDW data to determine the antibiotic prescribing patterns for respiratory tract infections and urinary tract infections (UTI) at VAST sites beginning January 1, 2019. We will then conduct a thorough medical record review on patients identified using CDW. Using this data, we will explore system factors, including prescriber specialty, to predict the rate of prescribing of antibiotics by race and ethnicity.

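### The effect of VAST overall (half of Aim 3) is assessed by an uncontrolled before/after comparison, although section 5.1 says control-site data will be reviewed

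*Combined protocol and SAP*

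**What the plan says.** - **Aim (section 3.0, Aim 3).** The aim is to "Determine the influence of the VAST overall and VAST+ on antibiotic use at each VAMC". For VAST overall the expectation is worded as a change over time with no comparator: "We anticipate that antibiotic use will decrease after VAST implementation at study sites".
- **Sites (section 5.1).** "The study will include up to 10 intervention sites, which are rural VA facilities". They are randomised to VAST- or VAST+, so every one of them receives VAST.
- **Control sites.** Section 5.1, under facility-level antibiotic use, states: "We will review total antimicrobial use at the intervention sites and at control sites". Section 5.4, under the same activity, states: "Information will be collected from CDW for all participating sites". It does not mention control sites.
- **Analysis (section 5.6, item 4).** "To assess for impact of VAST on antibiotic use, we will summarize the 4 antibiotic use metrics for each site", and this is done by "comparing the pre- and post-implementation periods for the acute and long-term care units". Each rate gets an exact Poisson 95% interval. The only model is a multi-level Poisson regression with facility as a random effect and arm, period and their interaction as fixed effects. The interaction is the effect of interest, and rate ratios are to be reported for each arm. No control site appears in it.
- **Monthly data (section 5.5, item 4).** Monthly values cover 12 months before and 15 months after the first session, with a 3-month wash-in. They serve to describe change, to understand month-to-month variability, and to flag data problems given "operational shifts occurring at facilities around COVID-19 treatment" or the Cerner rollout.

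**The concern.** A before/after contrast at sites that all receive the intervention cannot separate VAST from whatever else changed between the two windows. The plan itself expects such changes, namely COVID-19 operations and a new electronic record. The arm-specific rate ratios and the period term in the regression do not help, because they too compare VAST sites with themselves over time.

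At stake is one of the two questions of Aim 3, the aim that carries the primary outcome. A background fall would be credited to VAST, and a background rise would hide a real benefit. The design section already promises the data that could guard against this, but the analysis section does not use them.

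**Working it through.** The plan gives no alpha, power, baseline rate or days of care, so there is no figure of its own to reproduce. The volumes, drifts and standard deviations below are assumptions.

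**1. What each contrast estimates.** Let V be the true VAST rate ratio and B the background rate ratio between the two windows.
- Before/after at a VAST site: V × B.
- VAST+ versus VAST- interaction: (V₊ × B) / (V₋ × B) = V₊ / V₋. B cancels if it is common to both arms.
- Difference-in-differences against controls with the same B: (V × B) / B = V.

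With V = 1 and B = 0.95, the before/after ratio is 0.95, an apparent 5% reduction. With V = 0.95 and B = 1.05, it is 0.9975, and a real 5% reduction disappears. Neither result depends on site volume.

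**2. How often one site would look changed (V = 1, B = 0.95).** Assume equal days of care in two 12-month windows (15 − 3 = 12 after wash-in), with m₀ DOT before and m₁ = 0.95 m₀ after. The range of 500 to 8,000 DOT comes from an assumed 100 to 400 DOT per 1,000 days of care and 5,000 to 20,000 days of care per site-year.

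SE = √(1/m₀ + 1/m₁); z = |ln 0.95| / SE = 0.0513 / SE; P = Φ(z − 1.96) + Φ(−z − 1.96).

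| m₀ | m₁ | SE | z | P(interval excludes 1) |
|---|---|---|---|---|
| 500 | 475 | 0.0641 | 0.80 | 0.13 |
| 2,000 | 1,900 | 0.0320 | 1.60 | 0.36 |
| 3,000 | 2,850 | 0.0262 | 1.96 | 0.50 |
| 8,000 | 7,600 | 0.0160 | 3.20 | 0.89 |

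At 3,000 DOT the simpler SE of √(2/3,000) gives 0.51.

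**3. The same drift judged by the intervals the plan does specify.** Section 5.6 gives an interval for each rate, not for the ratio. Suppose a reader looks for non-overlap at 3,000 DOT. Approximating each interval as m ± 1.96√m, the intervals separate when the counts differ by more than 1.96 × (√3,000 + √2,850) = 1.96 × (54.77 + 53.39) = 212. The expected difference is 150, with SD √(3,000 + 2,850) = 76.5. So P = 1 − Φ((212 − 150)/76.5) = 1 − Φ(0.81) = 0.21.

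**4. What a control group would do.** A simulation of 20,000 runs used 10 VAST sites, 10 assumed control sites, 4,000 DOT per site-year, a site-by-period SD of 0.05 or 0.10 on the log scale, and no VAST effect.
- Background change 0, −5% and −10%: the mean before/after ratio was 1.00, 0.95 and 0.90. Difference-in-differences gave 1.00 throughout and rejected in 4.8% to 5.0% of runs.
- At −5%, a site-level paired t-test on the before/after change rejected in 50% of runs (SD 0.05) and 17% (SD 0.10).

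The simulation builds in a background change shared by VAST and control sites. It shows what controls achieve when that holds, not that it will hold.

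**The case against.** **The randomised comparison is sound.** The central hypothesis concerns the added value of feedback reports, and the interaction removes change common to both arms. This stands. A reader might infer that the VAST+ versus VAST- result is also biased by the missing controls, but the documents do not support that.

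**The plan only summarises.** Section 5.6 describes a per-site summary, and Aim 3 anticipates no more than a fall after implementation. It is true that no test is specified. But the stated purpose is to assess impact, so the causal reading is the plan's own.

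**False-signal rates are not the plan's.** This stands. A reader might infer that the plan would declare a 5% drift significant at about half the sites, or almost surely across ten. Section 5.6 sets no rate-ratio test, no decision rule and no pooled before/after analysis, and the documents give no DOT volumes. It also compares acute and long-term units, where counts would be smaller. Only the one-for-one bias is free of these assumptions.

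**Control data are not excluded.** Also fair. Section 5.4 names participating sites but does not say only those, so this is an inconsistency with section 5.1 rather than a prohibition. The monthly review gives partial protection against data disruption, though no adjustment of the estimate. A reader might also assume staggered start dates. The documents tie windows to each site's first session but do not say that the dates differ.

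**Conclusion.** The concern holds for VAST overall only. As written, that estimate is VAST multiplied by background change, in unknown proportion and direction. The conclusion rests on three facts in the text: every randomised site receives VAST, the impact assessment is before/after, and the promised control sites have no place in the analysis. The size of the bias equals the size of the background change, which the documents do not give.

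For a 5% fall with no VAST effect, the probability that one site's rate-ratio interval excludes 1 runs from 0.13 to 0.89 over an assumed 500 to 8,000 DOT per year. At 3,000 DOT it is about one half, or about 0.21 by non-overlap of the per-rate intervals. These are illustrations of scale, not operating characteristics of the plan.

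**What to change.** 1. **Reconcile sections 5.1, 5.4 and 5.6** on whether control-site data are collected and what they are for.
2. **Section 5.4:** include the control sites and define them before their data are examined, for example non-participating VAMCs without ID specialists, similar in bed numbers and complexity group. The 38 of 140 in section 2.0 counts healthcare systems in 2019, so the eligible number of rural VAMCs has to be established.
3. **Section 5.6:** estimate VAST overall by difference-in-differences or a controlled interrupted time series on the monthly rates. Give each control the start month and wash-in of its matched VAST site, adjust for calendar time, and use a variance that allows for facility-by-period variation.
4. **State the limits.** The method assumes parallel trends, which matters because sites are recruited through professional relationships (section 5.2). It does not remove disruptions specific to one site.

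**Cost.** Extra CDW extraction and analysis time, plus a check that data-access approvals cover control sites. Acute and long-term units at control sites must also be mapped without local champions, who supply unit names at intervention sites (section 5.5).

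**If control data cannot be obtained:** delete the control-site statement in section 5.1 and report VAST overall as a descriptive before/after change, not as an effect of VAST.
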